8.8 RATIONALE FOR STUDY

Allogeneic DC-based vaccination is a promising therapy option for the treatment of minimal residual disease in AML based on its mode of action as described above and the supportive results of the Phase I trial.

The next step in the development program is to try to obtain a clear efficacy signal based on a clinical parameter and to determine the magnitude of the clinical effect.

The primary endpoint for this study is to assess the effect of DCP-001 vaccination on MRD measured by flow cytometry as a surrogate marker for established clinical endpoints in AML pre- and post- vaccination. MRD evaluation is becoming the new standard in evaluating response in AML (17). Technical recommendations for MRD detection and its clinical use is supported by the European Leukemia Net (18).

The information obtained from this Phase II study will facilitate the design of a confirmatory Phase IIb study that includes linking of MRD to established clinical endpoints.

8.9 SELECTION OF DOSES IN THE STUDY

The Phase I study employed the traditional 3+3 design, starting with 10E6 cells per vaccination (3 patients), followed by 25E6 cells per vaccination (3 patients) and then 50E6 cells per vaccination (6 patients). In all three cohorts, immune responses were observed, as demonstrated by DTH responses, immunohistochemistry of biopsies of the DTH site, MLR, ELISpot and antibody responses. Not all parameters were measurable in all patients for a variety of reasons (e.g. insufficient material or technical difficulties). Preliminary analysis of the data indicated that the strongest immune responses were obtained in the middle cohort and highest dose cohort, but the study was too small to obtain a clear optimal dose signal between the mid and high dose.

Therefore, in the current study the safety and efficacy of both the mid (25E6 cells) and high dose (50E6 cells) will be established.

8.10 RISK-BENEFIT ASSESSMENT

In the Phase I study with DCP-001 the treatment was well tolerated, with no emerging potential safety issues

8.10.1 RISK OF INFECTION

Risk is considered low/absent as the DCOne cell line from which DCP-001 derived has been extensively tested for multiple viruses according to applicable regulatory guidelines (see IB). Upon release the DCP-001 product is confirmed to be sterile.

8.10.2 IMMUNE RESPONSE TO THE VACCINE

See section 8.7.1

8.10.3 INTRADERMAL INJECTION AND SKIN BIOPSY

Complications from intradermal injection as well as from the skin biopsy are likely to be minor.

8.10.4 BLOOD, BONE MARROW AND SKIN BIOPSY SAMPLING

This study involves frequent blood and bone marrow sampling. The total number and volume of blood samples is detailed in Table 4.

For immunomonitoring purposes, 70 mL of blood will be collected in heparin coated tubes. Samples will be taken at screening, start vaccination (d=0), day 44, day 77, day 128, day 140 and day 224.

For hematology diagnostic purposes, 21 mL of blood will be collected in heparin coated tubes.

Bone marrow aspirates (at least 3 ml or 16.106 cells for LAP analysis and 10 ml for biobanking) will be collected in heparin coated tubes. Samples will be taken at baseline (d=0), day 98, day 140, and at day 224. All BM samples should be obtained preferably from the first tap, gathered in heparin-coated tubes and kept at room temperature. In any case it should be indicated whether the sample is from the first or second tap. In addition, a single skin biopsy will be taken at 48h post 1st vaccination, 4th vaccination and 2nd booster vaccination. The biopsy will be 4-6 mm and will be taken using a standard punch needle. The injection site to be biopsied will be chosen at random and an injection site will be used for biopsy only once (no repeat biopsy of any injection site).

Table 4: Invasive procedures and sample sizes

| Visit no. | 1 | 2 | 3 | 4 | 5 | 6 | 7 | 8 | 9 | 10 | 11 | 12 | 13 |
|---|----|-----|----|-----|-----|-----|----|----|-----|-----|-----|-----|-----|
| Day | | 0 | 2 | 14 | 28 | 42 | 44 | 77 | 98 | 126 | 128 | 140 | 224 |
| quantity of Blood (mL) | | | | | | | | | | | | | |
| For diagnosis | 21 | 21 | | 21 | 21 | 21 | | | 21 | 21 | | 21 | 21 |
| For HLA classification | 24 | | | | | | | | | | | | |
| For immunomonitoring | | 70 | 70 | | | | 70 | 70 | | | 70 | 70 | 70 |
| quantity of Bone Marrow aspirate (mL) | | | | | | | | | | | | | |
| for diagnosis | | > 3 | | | | | | | > 3 | | | > 3 | > 3 |
| For biobank | | 10 | | | | | | | 10 | | | 10 | 10 |
| Vaccination | | | | | | | | | | | | | |
| number of intradermal injections ¹ | | 2-4 | | 2-4 | 2-4 | 2-4 | | | 1 | 1 | | | |
| Skin test | | | | | | | | | | | | | |
| number of biopsies ² | | | 1 | | | | 1 | | | | 1 | | |

1) Depending on dose: 2 for low dose, 4 for high dose and 1 for boosting dose

2) 1 biopsy to be taken from 1 injection site

9 STUDY OBJECTIVE(S) AND ENDPOINT(S)

The ultimate aim is to reduce the relapse risk through immune-mediated eradication of MRD, thereby prolonging relapse-free survival and overall survival.

9.1 STUDY OBJECTIVE(S)

9.1.1 Primary Objective(s)

1. To assess the effect of DCP-001 on MRD. MRD will be measured by flow cytometry pre and post vaccination as a surrogate marker for established clinical endpoints in AML.
2. To assess the effect of DCP-001 on immune responses in AML patients in first complete remission (CR1) and persistent MRD.
3. To document safety and tolerability.

9.1.2 Secondary Objective(s)

1. To identify surrogate (immunological) markers that might correlate with clinical outcome.
2. To quantify any lag time between initiation of treatment & onset of effect.
3. To determine the effect of DCP-001 on Time to Relapse (TTR).
4. To determine the effect of DCP-001 on Overall Survival (OS).
5. To document the difference between the two vaccination regimens based on MRD outcome and immunological parameters.

9.1.3 Exploratory Objectives

1. To document the number and duration of subsequent remissions.
2. To identify subgroups of patients most likely to benefit from treatment.

Immune monitoring:

Monitoring the immune response is an essential element to evaluate efficacy. The analysis of the immune response against tumour antigens in blood samples from these patients pre and post vaccination allows a better understanding of

1. the underlying mechanisms of action of the immunotherapy;
2. the prognostic value of immunological parameters; and
3. the use of new knowledge about immune parameters to design improved immunotherapy treatments for the future.

The following activities will be performed:

1. Antigen-specific T cell mediated immunity will be measured in PBMC by IFN- α ELISpot and intracellular cytokine release against antigens present in leukemic blasts and also known to be expressed by DCP-001 (i.e. PRAME, WT-1, MUC1, RHAMM). Both pre-and various time points post-vaccination will be analysed.
2. Changes in profiles of different PBMC populations. This includes T-cell profiles, regulatory T cells, MDSC, NK cells etc., according to the same schedule as for antigen-specific responses.
3. General T-cell activation capability and thus immune competence of patients will be analysed by measuring T-cell proliferation and cytokine release following stimulation with DCP-001 in vitro. Pre- and post-vaccination samples will be compared.

4. Biopsies will be taken from the injection site and analysed for specified markers in order to identify the local immune infiltration process.

9.2 ENDPOINTS

9.2.1 Primary Efficacy Endpoint

- The effect of DCP-001 on MRD levels as a surrogate marker for established clinical endpoints in AML.
- To assess the effect of DCP-001 on immune responses in AML patients in first complete remission (CR1) with MRD.
- To document safety and tolerability.

9.2.2 Secondary Efficacy Endpoints

- To identify surrogate (immunological) markers that might correlate with clinical outcome.
- To quantify any lag time between initiation of treatment & onset of effect.
- To determine the effect of DCP-001 on Time to Relapse (TTR).
- To determine the effect of DCP-001 on Overall Survival (OS).
- To document the difference between the two vaccination regimens based on MRD outcome and immunological parameters.

9.2.3 Exploratory Endpoints

- To document the number and duration of subsequent remissions.
- To identify subgroups of patients most likely to benefit from treatment.
- To identify surrogate (immunological) markers that might correlate with clinical outcome.
- To quantify any lag time between initiation of treatment & onset of effect.

9.2.4 Safety endpoints:

- Treatment emergent adverse events (TEAEs) will be collected in first 48 hours after the first vaccination to determine (acute) toxicity due to intradermal injection.
- All TEAEs will be collected during the study period for each patient and the grade of toxicity (CTCAE v.4.0, see Appendix B) and relationship to product determined.
- A DSMB will meet after every 5 patients complete treatment to evaluate safety; written reports will be made of each meeting. Additional details are provided in the DSMB charter.
- All SAEs will be reported by the investigator within 24 hours of the first knowledge. All SAEs will be reported in a timely manner to the appropriate regulatory body, consistent with applicable regulations. Information on relevant SAEs will be disseminated between sites in a timely manner. Processes are described in detail in the study specific safety plan.
- The safety will include all subjects signing ICF and efficacy databases will include only those subjects included in the study who received at least one vaccination.

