| 
Duration of treatment:
 
4 vaccinations at biweekly intervals, followed by two booster vaccinations 8 and 12 weeks after the 4th (week 6) vaccination. Total treatment duration 18 weeks.
 |
| 
Reference therapy, dosage and mode of administration:
 
N.A.
 |
| 
Criteria for evaluation:
 
1. Any change in MRD (flow cytometric) as compared to baseline MRD2. Any change in immunoreactivity (specific and non-specific) as compared to baseline. |
| 
Safety endpoints:
 
1. Treatment emergent adverse events (TEAEs) will be collected in the first 48 hours after the first vaccination to determine (acute) toxicity due to intradermal injection.2. All TEAEs will be collected during the study for each patient and the grade of toxicity using Common Terminology Criteria for Adverse Events (CTCAE V4) and relationship to product determined.3. A Data Safety Monitoring Board (DSMB) will meet after every 5 patients treated to evaluate safety; written reports will be made of each meeting.4. All Serious Adverse Events (SAEs) will be reported by the investigator within 24 hours of first knowledge. All SAEs will be reported in a timely manner to the appropriate regulatory body, consistent with existing regulations. Information on relevant SAEs will be disseminated between sites in a timely manner.5. The safety and efficacy databases will include only the subjects included in study and received a least one vaccination. |

Statistical Methods:

Sample Size Assumptions: The planned sample size of 20 evaluable subjects will be distributed 1:1 with 10 subjects each in Group 1 - 25E6 DCP-001 cells per vaccination, and Group 2 - 50E6 DCP-001 cells per vaccination. Additional subjects may be enrolled to ensure that 20 evaluable subjects complete the study. The sample size is based on practical considerations, rather than strict sample size statistical considerations with a desired power for a pre-specified difference.

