T-cell reactivity by IFN γ ELISpot analysis after *in-vitro* stimulation was assessed against the AML-related antigens WT-1 and PRAME, both of which were expressed by the DCP-001 vaccine, as well as against NY-ESO-1 and MAGE-A3. NY-ESO-1 and MAGE-A3 were not expressed by DCP-001 but were included to monitor for possible epitope spreading. All tested patients showed pre-existent reactivity to the CEFT recall antigen pool, which was maintained over treatment, indicating good immune competence. Four out of eight evaluable patients showed DCP-001 induced or enhanced WT-1, PRAME, MAGE-A3, or NY-ESO-1 responses (Table 3).

Antibody responses

Antibody responses generated against DCOne progenitor and autologous blast antigens was evaluated in 10/12 patients. 5 patients showed an increased response denoting antigen-specific humoral responses. Induced antibody responses against autologous blasts were observed in two out of three evaluable patients, which demonstrates the induction of immunity against autologous AML blasts by the allogeneic DCP-001 vaccine.

DTH reactivity

In the DTH tests, 5 of 11 evaluable patients had an increase of $\geq 50\%$ in the mean diameter of induration at day 51 compared to baseline (i.e. positive according to criteria formulated), indicating the induction of a T-cell-mediated response to DCP-001 (Table 3). No reactivity to the Cryostor vehicle control was ever observed (data not shown). Of the 7 patients who did not have an increase at day 51 compared to baseline, all showed a baseline reaction of at least 4mm (range 3.5-15mm). A measurable DTH response at baseline indicates pre-existing immunity to components of the DCP-001 vaccine. This could be an allo-reaction, but could also be a response to TAAs in the vaccine. Evidence for vaccination-induced increases in DTH reactivity was mostly found among long-term (>6 months) survivors (Table 3).

Immunohistochemistry

Immunohistochemical assessment of DTH punch biopsies was performed for T-cell and DC influx in 9 out of 12 patients at day 2 and day 51. All of these patients showed an increased influx of activated T-cells in response to the vaccine as compared to the Cryostor vehicle control.

T-cell reactivity to DCP-001 and its DCOne progenitors by MLR

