12.3 DOSE LEVELS

Patients will receive 25E6 DCP-001 cells per vaccination (Group 1; 10 patients) or 50E6 DCP-001 cells (Group 2; 10 patients) per vaccination. Both groups will receive two additional booster vaccination of 10E6 cells.

The first treatment for both dose groups is given at Day 0 (Baseline), the second, third and fourth treatments are given at 2 weekly intervals. A total of 4 treatments will be administered in a 6 week timeframe followed by a booster vaccination at 8 and 12 weeks after the 4th vaccination at week 6. A summary of the treatment schedule is given below:

Groups 1 and 2;

Day 0 1st vaccination with 25E6 or 50E6 cells.

Week 2 2nd vaccination with 25E6 or 50E6 cells.

Week 4 3rd vaccination with 25E6 or 50E6 cells.

Week 6 4th vaccination with 25E6 or 50E6 cells.

Week 14 and 18 booster vaccination with 10E6 cells.

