- Skin biopsy from 1 out of the 2 or 4 injection sites for evaluation of immunological response in skin biopsy.
- Blood sample collection for immunological response
- Record any AEs, SAEs and concomitant medications and/or changes in ongoing AEs, SAEs and ongoing concomitant medications
- Day is fixed with the previous visit (Visit 6)

Treatment Period (Visit 8)/ day 77

according to the assessment schedule \pm 3 days

- Physical examination, ECOG and Vital signs
- Record any new AEs, SAEs and concomitant medications and/or changes in ongoing AEs, SAEs and ongoing concomitant medications
- Blood sample collection for immunological response

Treatment Period (Visit 9-10)/days 98, 126

according to the assessment schedule \pm 3 days

- Physical examination, ECOG and Vital signs
- Hematology and biochemistry
- Record any new AEs, SAEs and concomitant medications and/or changes in ongoing AEs, SAEs and ongoing concomitant medications.
- Administration of study medication (DCP-001 booster vaccination)
- **Visit 9;** Bone marrow aspirate for MRD analysis (MRD assessment) and biobanking

Treatment Period (Visit 11)/day 128

- Skin biopsy from 1 out of the 2 or 4 injection sites for evaluation of immunological response in skin biopsy
- Blood sample collection for immunological response (immunomonitoring)
- Record any new AEs, SAEs and concomitant medications and/or changes in ongoing AEs, SAEs and ongoing concomitant medications
- Day is fixed with the previous visit (visit 10)

Treatment Period (Visit 12)/day 140

according to the assessment schedule \pm 3 days

- Physical examination, ECOG and Vital signs
- Hematology and biochemistry
- Record any AEs, SAEs and concomitant medications and/or changes in ongoing AEs, SAEs and ongoing concomitant medications.
- Bone marrow aspirate for MRD analysis (MRD assessment) and biobanking
- Blood sample collection for immunological response (immunomonitoring)

Treatment Period (Visit 13)/ day 224

according to the assessment schedule \pm 3 days

- Physical examination, ECOG and Vital signs
- Hematology and biochemistry
- Record any new AEs, SAEs and concomitant medications and/or changes in ongoing AEs, SAEs and ongoing concomitant medications.
- Bone marrow aspirate for MRD analysis (MRD assessment) and biobanking
- Blood sample collection for immunological response

Follow-up visits (14-17)

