16.2.4 Safety analyses

AEs will be classified as treatment emergent AEs (TEAEs) if they start on or after the first vaccination, through 30 days after the last vaccination. AEs that are present prior to the first vaccination, but their severity or relationship increases after the first vaccination, will also be classified as TEAEs.

TEAEs will be tabulated using MedDRA body system and preferred term. The number and percentage of subjects experiencing at least one TEAE overall and at least one TEAE for a body system and preferred term will be tabulated by toxicity grade (CTCAE) and treatment group. A similar summary will be completed by relationship to study product and treatment group. For the calculations in these tables, each subject's TEAEs will be counted once under the maximum toxicity grade or the strongest recorded causal relationship to study product. A summary will be performed for all serious TEAEs. A listing of SAEs will provide details of the events including severity, relationship to study product, time between onset and last vaccination, number of vaccinations received, and a summary of the event. A summary and listing will also be presented for TEAEs causing treatment discontinuation.

Clinical Laboratory results will be summarized descriptively for each treatment group by visit for the observed value as well as for the change from baseline value. In addition, laboratory shift tables will be provided for all laboratory parameters where low/normal/high or abnormal/normal status can be ascertained. In the event of repeat values, the last non-missing value per study day/time will be used for summarization. Listings of individual laboratory parameters by visit with normal ranges and abnormality assessments will also be completed by subject. Laboratory listings will include the study day, date collected, and observed laboratory values with out-of-range values flagged. Unscheduled visit laboratory results will not be summarized but will be included in patient data listings.

For vital signs, descriptive statistics of observed values will be presented for each scheduled visit by treatment group. Changes from baseline to each scheduled post-baseline visit will be presented. All vital sign data by subject will be presented in a listing. Unscheduled visit vital sign data will not be summarized but will be included in patient data listings.

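### The acute-toxicity endpoint covers only the 48 hours after the first of six administrations, so it cannot show acute reactions after doses 2 to 4 or after either booster

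*Protocol*

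**What the plan says.** Section 9.2.4 opens its safety endpoints with this sentence: "Treatment emergent adverse events (TEAEs) will be collected in first 48 hours after the first vaccination to determine (acute) toxicity due to intradermal injection". The synopsis limits the window in the same way: TEAEs "will be collected in the first 48 hours after the first vaccination to determine (acute) toxicity due to intradermal injection".

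The next item in 9.2.4 is broader: "All TEAEs will be collected during the study period for each patient and the grade of toxicity", together with relationship to product. Section 16.2.4 counts an event as treatment emergent from the first vaccination to 30 days after the last. In its tables, "each subject's TEAEs will be counted once under the maximum toxicity grade or the strongest recorded causal relationship to study product". Time since the last vaccination and number of vaccinations received appear only in the listing of SAEs.

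On dosing, 12.3 states: "A total of 4 treatments will be administered in a 6 week timeframe followed by a booster vaccination at 8 and 12 weeks". The footnote to Table 4 gives the number of injections: "Depending on dose: 2 for low dose, 4 for high dose and 1 for boosting dose". Section 12.4 requires at least 60 minutes of observation after each vaccination. Table 1 and 14.1 schedule visits with AE recording on Days 2, 44 and 128, each fixed relative to the visit before it.

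Safety and tolerability is a primary objective (9.1.1) and is also listed under the primary endpoint (9.2.1).

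**The concern.** DCP-001 is given repeatedly in order to build an immune response. The first dose cannot show a reaction that depends on sensitisation by earlier doses, yet it is the only dose that the acute endpoint looks at. Phase I gave four vaccinations and no booster, so how the boosters are tolerated is new information, and this endpoint contains none of it.

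The protocol's Phase I data give some reason to look beyond dose 1. In the DTH test, 5 of 11 evaluable patients showed growth of at least 50%, described as an increase "in the mean diameter of induration at day 51 compared to baseline (i.e. positive according to criteria formulated), indicating the induction of a T-cell-mediated response" (8.7.1).

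At stake is whether the report can answer a simple question under a primary objective: do acute reactions change in frequency or grade as dosing proceeds, and what happens after a booster? Section 15.8 makes safety before the next vaccination the main task of the DSMB, and that task raises the same question.

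**Working it through.** The protocol gives no figure for this endpoint, so there is none to reproduce. The check counts what the endpoint covers, looks at what Phase I can support, and asks which visits could serve a wider endpoint.

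**1. Share of dosing covered.** Inputs: four vaccinations and two boosters per patient, with 25E6 or 50E6 cells per vaccination and 10E6 per booster (12.3); 2, 4 or 1 injections per administration (Table 4); 10 patients per group (section 10).

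- Dosing windows: 1/6 = 17%. Over 20 patients this is 20 of 20 × 6 = 120 patient-administrations, and 0 of 20 × 2 = 40 booster administrations.
- Injections, Group 1: 4 × 2 + 2 × 1 = 10, of which 2 are covered (20%).
- Injections, Group 2: 4 × 4 + 2 × 1 = 18, of which 4 are covered (22%).
- Cells, Group 1: 25E6 of 4 × 25E6 + 2 × 10E6 = 120E6 (21%).
- Cells, Group 2: 50E6 of 4 × 50E6 + 2 × 10E6 = 220E6 (23%).

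These are shares of exposure, not of toxicity missed. The six windows are also unequal, because a booster is a single injection of 10E6 cells.

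**2. What Phase I supports.** Growth in induration: 5/11 = 45%, exact (Clopper-Pearson) 95% interval 17% to 77%. Section 8.7.1 also describes 7 patients without an increase, and 5 + 7 = 12, not 11. With 12 as denominator the rate is 42% (15% to 72%). On either count, growth was seen in fewer than half. DTH is an immune readout and not an adverse-event rate, and the patients without growth already had a measurable baseline reaction.

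**3. First window against all six (illustration only).** The protocol gives no per-dose risk of an acute event. Assume a constant, independent risk p per administration, which the unequal doses make crude. The proportion of patients with at least one acute event over six windows is 1 − (1 − p)^6.

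| p (first window) | all six windows |
|---|---|
| 5% | 26% |
| 10% | 47% |
| 20% | 74% |
| 30% | 88% |

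Even with no sensitisation at all, a first-dose result therefore does not describe the course of six. The table does not estimate what this trial would miss.

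**4. Visits that could serve a wider endpoint.** Table 1, 12.3 and 14.1 put the boosters at weeks 14 and 18, that is Days 98 and 126 (Day 42 + 56 and Day 42 + 84). The fixed 48-hour visits then follow doses 1, 4 and 6, which gives 3 × 20 = 60 patient-administrations. Section 12.4 puts the boosters on Days 77 and 98. On those days, Day 128 would fall 30 days after the second booster, no booster would have a 48-hour visit, and the count would be 2 × 20 = 40. The two statements cannot both hold.

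**The case against.** The strongest reply is that nothing is lost. All TEAEs are a safety endpoint in their own right, graded and related to product, and are tabulated to 30 days after the last vaccination. There is a separate summary of TEAEs leading to discontinuation, patients are observed after every dose, and the DSMB reviews safety after every five patients. Counting a subject once at maximum grade lets a worse later reaction replace a milder first one, so the rule hides timing and not severity. A table by dose number is the kind of detail that 16.2.4 leaves to the statistical analysis plan.

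Most of this stands. A reader might infer that the trial's safety data understate the toxicity of the regimen. They do not, because later acute events enter the overall TEAE tables. A reader might also infer that Phase I shows local reactions growing with repeated dosing, so that acute reactions are to be expected mainly after later doses. The documents do not support that either. The evidence is a skin test that rose in 5 of 11 evaluable patients. Pre-existing reactivity was common: 7 of 9 tested patients had prior T-cell responses to the vaccine or its progenitor cells. Treatment is described as well tolerated. Part of the Phase I safety account in 8.7.1 was not available for this check, so local reactions by dose number could not be examined.

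The reply fails on one point. The restriction to the first vaccination is written into the endpoint itself, in two places in the protocol. An analysis plan can add a table, but it would then be reporting something other than the endpoint the protocol defines.

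**Conclusion.** The point holds in a limited form. As worded, the endpoint labelled as determining acute toxicity sees 1 of 6 dosing windows and no booster. It cannot show reactions that depend on earlier doses or arise after boosting. For non-serious events, the summaries described in 16.2.4 do not fill the gap, because they carry neither dose number nor time since dose.

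The gap concerns one labelled endpoint and its interpretation, not the completeness of the safety data. The size of any understatement in that endpoint cannot be derived from the protocol, since no acute-event rate by dose is available. The coverage figures assume that all 20 patients receive all six administrations; patients who stop early would raise the covered share. The change should be made because safety is a primary objective and the data needed are already being collected.

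**What to change.** - In 9.2.4 and the synopsis, define the endpoint as TEAEs with onset within 48 hours after each vaccination and each booster. If the first dose alone is intended, state why it is enough.
- In 16.2.4, tabulate these events by administration number (1 to 6) and dose group. Note that each booster is a single injection of 10E6 cells, so the windows are not alike in exposure.
- Mark in the table which administrations have a fixed 48-hour visit and which rely on recall at the next visit.
- Before Day 128 is used as the 48-hour visit after the second booster, reconcile the booster days in 12.4 (Days 77 and 98) with those in Table 1, 12.3 and 14.1 (Days 98 and 126, weeks 14 and 18).
- In 8.7.1, reconcile the 11 evaluable DTH patients with the 5 and 7 described.

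The cost is one sentence in two places and one extra table. AEs are already recorded at every visit, so the table needs only their onset dates and no new procedure. The downside is weaker ascertainment after doses 2, 3 and 5, which have no 48-hour visit under Table 1.
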